## APPENDIX E. EXAMPLES OF STRONG CYP2D6 INHIBITORS, STRONG CYP3A4 INDUCERS, MEDICATIONS THAT PROLONG QT INTERVAL, AND CENTRALLY ACTING H1R ANTAGONISTS

Medication Type	Examples
Strong CYP2D6 inhibitors	paroxetine, fluoxetine, bupropion, quinidine, terbinafine
Strong CYP3A4 inducers	rifampin, carbamazepine, phenytoin, apalutamide, St John's wort, enzalutamide, mitotane
Medications that prolong QT Interval	Class 1A antiarrhythmics : quinidine, procainamide, disopyramide
	Class 3 antiarrhythmics: amiodarone, sotalol, dofetilide
	Antipsychotics: ziprasidone, chlorpromazine, thioridazine, haloperidol
	Antibiotics: moxifloxacin, ciprofloxacin, erythromycin, ketoconazole
Centrally acting H 1 R antagonists (sedating or lipophilic H 1 R antagonists)	pheniramine maleate, diphenhydramine, promethazine (anti- histamines) imipramine, clomipramine, mirtazapine (tri or tetracyclic antidepressants)

CYP = cytochrome P450;  $H_1R$  = histamine 1 receptor

## APPENDIX F. DAYTIME SLEEPINESS SCALE (DSS)

### DAYTIME SLEEPINESS SCALE

For each statement, circle the number that best corresponds to what you are currently experiencing.

		Never or almost never	Sometimes	Often	Always or almost always
1.	I take one or more naps during the day.	0	1	2	3
2.	I occasionally have a sudden urge to sleep during the day.	0	1	2	3
3.	I occasionally fall asleep in front of the television or at the movies.	0	1	2	3
4.	I have difficulty remaining still for long periods of time.	0	1	2	3
		Always or almost always	Often	Sometimes	Never or almost never
5.	I am generally in great shape during the day.	0	1	2	3

Please note that question #5 is scored in the reverse order.

Total Score: \_\_\_\_\_

Daytime Sleepiness Scale Version date 12Nov2021

## **APPENDIX G. FATIGUE SEVERITY SCALE (FSS)**

## Fatigue Severity Scale

Below are a series of statements regarding your fatigue. By fatigue we mean a sense of tiredness, lack of energy or total body give-out. Please read each statement and choose a number from 1 to 7, where # 1 indicates you completely disagree with the statement and # 7 indicates you completely agree. Please answer these questions as they apply to the past **TWO WEEKS**.

		Completely Disagree					С	completely Agree
1.	My motivation is lower when I am fatigued	1	2	3	4	5	6	7
2.	Exercise brings on my fatigue	1	2	3	4	5	6	7
3.	I am easily fatigued	1	2	3	4	5	6	7
4.	Fatigue interferes with my physical functioning	1	2	3	4	5	6	7
5.	Fatigue causes frequent problems for me	1	2	3	4	5	6	7
6.	My fatigue prevents sustained physical functioning	1	2	3	4	5	6	7
7.	Fatigue interferes with carrying out certain duties and responsibilities	1	2	3	4	5	6	7
8.	Fatigue is among my 3 most disabling symptoms	1	2	3	4	5	6	7
9.	Fatigue interferes with my work, family, or social life	1	2	3	4	5	6	7

© 1985 Lauren B. Krupp. Reproduced with permission from the author.

FSS - United States/English - Mapi Institute. ID8492/FSS\_TS1.0\_eng-USori.doc

## APPENDIX H. MYOTONIC DYSTROPHY HEALTH INDEX (MDHI)

# THE MYOTONIC DYSTROPHY HEALTH INDEX (MDHI)

Copyright 2012 [name], MS-CI

Date: Initials: Visit #: Study:

Participant #:

### THE MYOTONIC DYSTROPHY HEALTH INDEX

Directions	Please c	heck the	how that	annlies to	you for each item.
Duccuons.	T ICHOU C	neek ine	oox mat	appuesto	you for cach field.

1. How much does the following impact your life now?	I don't experience this	I experience this but it does not affect my life	It affects my life a little	It affects my life moderately	It affects my life very much	It affects my life severely
a.) Limitations with your mobility or walking						
b.) Problems with your hands or arms						
c.) Inability to do activities						
d.) Fatigue						
e.) Pain						
f.) Gastrointestinal issues						
g.) Problems with your vision						
h.) Communication difficulties						
i.) Impaired sleep or daytime sleepiness						
j.) Emotional issues						
k.) Difficulty thinking						
1.) Decreased satisfaction in social situations						
m.) Decreased performance in social situations						
n.) Myotonia						
o.) Breathing difficulties						
p.) Choking or swallowing issues						
q.) Hearing difficulties						

2. How much does the following impact your life now?	I don't experience this	I experience this but it does not affect my life	It affects my life a little	It affects my life moderately	It affects my life very much	It affects my life severely
a.) Difficulty staying in a standing position						
b.) Difficulty walking long distances						
c.) Difficulty with stairs						
d.) Inability to walk fast						
e.) Difficulty with balance						
f.) Impaired walking						
g.) Difficulty rising from a seated position						
h.) Inability to run						
i.) Ankle weakness						
j.) Tripping						
k.) Falls						
1.) Difficulty getting up from a lying position						

3. How much does the following impact your life now?	I don't experience this	I experience this but it does not affect my life	It affects my life a little	It affects my life moderately	It affects my life very much	It affects my life severely
a.) Hand weakness						
b.) Difficulty doing things with your hands						
c.) Difficulty lifting objects						
d.) Difficulty picking things up with your fingers						
e.) Arm weakness						
f.) Problems reaching things over your head						
g.) Droopy eyelids						
h.) Facial weakness						
i.) Neck weakness						
j.) Impaired ability to open doors or drawers						

4. How much does the following impact your life now?	I don't experience this	I experience this but it does not affect my life	It affects my life a little	It affects my life moderately	It affects my life very much	It affects my life severely
a.) Difficulty opening jars or bottles						
b.) Difficulty playing sports						
c.) Trouble going up step ladders						
d.) The inability to keep pace with friends while walking						
e.) Impaired dancing						
f.) Impaired ability to exercise						
g.) Difficulty using a hammer or other tool						
h.) Taking longer to do household chores						
i.) Impaired sexual function						
j.) Problems using buttons or zippers						
k.) Difficulty scrubbing surfaces						
1.) Difficulty cleaning a home						
m.) A change in your activities because of gastrointestinal symptoms						

5. How much does the following impact your life now?	I don't experience this	I experience this but it does not affect my life	It affects my life a little	It affects my life moderately	It affects my life very much	It affects my life severely
a.) Poor handwriting						
b.) Slurring of your speech						
c.) Impaired facial expression						
d.) Difficulty communicating with others						
e.) Quiet voice						
f.) Tongue cramping						

## Protocol No: HBS-101-CL-005, Amendment 5 Phase 2 Safety and Efficacy Study

6. How much does the following impact your life now?	I don't experience this	I experience this but it does not affect my life	It affects my life a little	It affects my life moderately	me very	It affects my life severely
a.) Inability to do things that you used to do						
b.) Self-conscious of muscle loss						
c.) Perceived burden to family members						
d.) Increased family stress						
e.) Dissatisfaction with social interactions						

7. How much does the following impact your life now?	I don't experience this	I experience this but it does not affect my life	It affects my life a little	It affects my life moderately	It affects my life very much	It affects my life severely
a.) The reliance on family members						
b.) Decreased independence						
c.) Inability to care for family members						
d.) The avoidance of social situations						
e.) Impaired social interactions						
f.) Difficulty with relationships						

8. How much does the following impact your life now?	I don't experience this	I experience this but it does not affect my life	It affects my life a little	It affects my life moderately	It affects my life severely
a.) Decreased energy					
b.) Impaired endurance					
c.) Tired muscles					

9. How much does the following impact your life now?	I don't experience this	I experience this but it does not affect my life	It affects my life a little	It affects my life moderately	It affects my life very much	It affects my life severely
a.) Back pain						
b.) Muscle stiffness						
c.) Leg pain						
d.) Limited activity from pain						
e.) Muscle cramping						
f.) Pain all over						
g.) Arm pain						

### Protocol No: HBS-101-CL-005, Amendment 5 Phase 2 Safety and Efficacy Study

10. How much does the following impact your life now?	I don't experience this	I experience this but it does not affect my life	It affects my life a little	It affects my life moderately	It affects my life very much	It affects my life severely
a.) Hand myotonia						
b.) Myotonia all over						
c.) Jaw stiffness (myotonia)						

11. How much does the following impact your life now?	I don't experience this	I experience this but it does not affect my life	It affects my life a little	It affects my life moderately	It affects my life very much	It affects my life severely
a) Diarrhea						
b.) Constipation						
c.) Gas						
d.) Abdominal pain						
e.) Stomach cramping						

12. How much does the following impact your life now?	I don't experience this	I experience this but it does not affect my life	It affects my life a little	It affects my life moderately	It affects my life severely
a.) Problems swallowing					
b.) Fear of choking					

13. How much does the following impact your life now?	I don't experience this	I experience this but it does not affect my life	It affects my life a little	It affects my life moderately	mevery	It affects my life severely
a.) Poor night vision						
b.) Visual loss						
c.) Eye irritation						

14. How much does the following impact your life now?	I don't experience this	I experience this but it does not affect my life	It affects my life a little	It affects my life moderately	It affects my life very much	It affects my life severely
a.) Frustration						
b.) Reduced enjoyment with activities						
c.) Fear of injury with activity						
d.) Depression						
e.) Damaged pride with loss of independence						
f.) Feeling overwhelmed						
g.) Moodiness						
h.) Increased stress						
i.) Anxiety						
j.) Impaired self-image						
k.) Anger						

15. How much does the following impact your life now?	I don't experience this	I experience this but it does not affect my life	It affects my life a little	It affects my life moderately	It affects my life severely
a.) Daytime sleepiness					
b.) Excessive sleep requirements					
c.) Difficulty falling asleep at night					

16. How much does the following impact your life now?	I don't experience this	I experience this but it does not affect my life	It affects my life a little	It affects my life moderately	It affects my life severely
a.) Decreased motivation					
b.) Fear of a worsening ability to think					
c.) Thinking fatigue					
d.) Decreased ability to think fast					
e.) Memory problems					
f.) Disorganization					
g.) Problems concentrating					
h.) Difficulty with comprehension					

## END OF SURVEY

## **APPENDIX I. EPWORTH SLEEPINESS SCALE (ESS)**

### **Epworth Sleepiness Scale**

Name:	Today's date:
Your age (yrs):	Your gender (Male = M, Female = F):

How likely are you to doze off or fall asleep in the following situations, in contrast to just feeling tired?

This refers to your usual way of life recently.

Even if you haven't done some of these things recently, try to figure out how they would have affected you.

Use the following scale to choose the most appropriate number for each situation:

0 = no chance of dozing
1 = slight chance of dozing
2 = moderate chance of dozing
3 = high chance of dozing

It is important that you answer each item as best as you can.

Chance of Dozing (0-3)

\_\_\_\_

#### Situation

Sitting and reading	
Watching TV	_
Sitting inactive in a public place (e.g., a theater or a meeting)	_
As a passenger in a car for an hour without a break	_
Lying down to rest in the afternoon when circumstances permit	_
Sitting and talking to someone	_
Sitting quietly after a lunch without alcohol	
In a car or bus, while stopped for a few minutes in traffic	

#### THANK YOU FOR YOUR COOPERATION

ESS © MW Johns 1990-1997. Used under License

ESS - United States/English - Version of 19 Jan 18 - Mapi. ID037309 / ESS AU1.0 eng-US2.doc

## APPENDIX J. CLINICAL GLOBAL IMPRESSION OF SEVERITY (CGI-S) FOR EXCESSIVE DAYTIME SLEEPINESS

## APPENDIX K. PATIENT GLOBAL IMPRESSION OF SEVERITY (PGI-S) FOR EXCESSIVE DAYTIME SLEEPINESS

## 2 Change History

The table below details changes from the prior approved version of the statistical analysis plan (SAP).

Version/Date	Change Log
1.0 / 27-Apr-2021	Created as new
2.0 /03Nov2023	
Section 6.0: Updated the protocol version and the change of CRO name.
 
Section 6.1: Added justification to indicate that treatment is summarized by total treatment in the Open-Label Extension Phase of the study.
 
Section 8.1: Updated the section to match changes in the protocol to the duration of (i.e. to define the end of the Open-Label Extension Phase of the study).
 
Section 8.2:
 
 
Removed sample size and statistical power estimation.
 
Updated the section to match changes in the protocol to the sample size considerations.
 
 
Section 8.3: Added stratification factor in the randomization.
 
Section 9.1:
 
 
Updated the section to match changes in the protocol to the primary efficacy endpoint.
 
Removed Z-score (aggregation of Daytime Sleepiness Scale [DSS] and Mean Sleep Latency [MSL]) endpoint
 
 
Section 9.2.1:
 
 
Updated visit window in the Double-Blind Treatment Phase to be identical across assessments.
 
Updated visit window schedule for the Open-Label Extension Phase (last visit is now visit 8 / Month 15).
 
Updated Visit label to include the visit number and study day/month.
 
Added rules for revising study day, if there is a re-start in dose escalation in the Double-Blind Treatment Phase.
 
 
Section 10.0: Clarified the analysis population and treatment group for the Open-Label Extension Phase.
 
Section 10.3: Updated details on how the patients will be summarized.
 
Section 10.4: Revised PK population definition to match the protocol.
 
Section 10.5: Removed Maintenance of Wakefulness Test (MWT) population
 
Section 11.0: Updated the section to match changes in the protocol.
 
Section 11.1.1: Revised to add screen failure details and patient disposition with respect to treatment and study during the Open-Label Extension Phase.
 
Section 11.1.2: Clarified summary for Double-Blind Treatment Phase and overall for the OLE Phase.
 
Section 11.1.3: Clarified that the failed inclusion/exclusion criteria for randomized patients will be listed.
 
Section 11.2.3: Removed summary for the seizure history, as it is not required.
 
Section 11.3.3: New added section to provide details on identifying wake-promoting agents.
 
Section 11.4: Clarified that wake-promoting agents at randomization will also be derived from the database.
 
Added stratification factor to inferential model. In addition, minor reorganization to section numbering to accommodate revisions to match changes in the protocol.
 
Section 11.4.1:


	

• Updated the section to match changes in the protocol.

• Replaced Analysis of Covariance (ANCOVA) with Mixed Model Repeated Measures (MMRM) for primary endpoint analysis method

 
Section 11.4.1.1: Updated pooling strategy to clarify the pooled active groups.
 
Section 11.4.3: Removed analysis of site effect in statistical models for study endpoint analysis.
 
Section 11.4.3.1.2: Removed multiple imputation (MI) and sensitivity analyses
 
Section 11.6.1: Included summary by system organ and class and preferred term for all adverse events and all serious adverse events.
 
Section 11.6.3: Added details on imputation of results reported as “<xx” or “>xx”.
 
Section 11.6.4: Added vital sign reference ranges and shift table summary. Removed abnormal criteria and associated summary.
 
Appendix 4: Added stratification factor in SAS code examples.

--	---

## 4 Purpose

The Statistical Analysis Plan (SAP) describes the statistical methods to be used during the analyses and reporting of data collected under Harmony Biosciences, LLC, Protocol HBS-101-CL-005.

## 5 Scope

The SAP outlines the following:

- Study Objectives
- Study Design
- Endpoints
- Applicable Study Definitions
- Statistical Methods

## 6 Introduction

This SAP should be read in conjunction with the study protocol Amendment 5 dated 18 July 2023 and electronic case report form (eCRF) v4.0 dated 09May2023. Any changes to the protocol or eCRF may necessitate updates to the SAP.

The SAP Version 1 was approved on 28 April 2021. This SAP Amendment 1 (Version 2.0) will include changes to the protocol through protocol Amendment 5. Final approval of the SAP by Harmony Biosciences, LLC and ICON will occur prior to the database entry lock and unblinding of the database for the analyses of the Double-Blind Treatment Phase of the study.

If the statistical analyses described in the final SAP and final protocol differ, the statistical analyses in the SAP will be used for the analyses presented in the clinical study report (CSR). Substantive changes from the analyses specified in the protocol will be described in the SAP and in the CSR.

### 6.1 Changes from Protocol

The Intent-to-Treat Population referenced in protocol Amendment 4 is referred to as the modified Intent-to-Treat Population (mITT) in the SAP; the definition remains same.

For the Open-Label Extension (OLE) Phase reporting, all patients will be analyzed as a single group, which will be labelled "Total". All patients will be titrated during a 3-week Titration Period to a dose of 35.6 mg pitolisant (or a maximum dose up to 35.6 mg based on Investigator assessment of tolerability). Additional changes from protocol Amendment 4 include:

- Removed sample size and statistical power calculation
- Removed Z-score (aggregation of Daytime Sleepiness Scale [DSS] and Mean Sleep Latency [MSL]) endpoint
- Removed Maintenance of Wakefulness Test (MWT) population
- Replaced Analysis of Covariance (ANCOVA) with Mixed Model Repeated Measures (MMRM) for primary endpoint analysis method
- Removed analysis of site effect in statistical models for study endpoint analysis
- Removed multiple imputation (MI) and sensitivity analyses

---

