# 9. STATISTICAL CONSIDERATIONS

# 9.1. General Considerations

All safety and efficacy data will be listed and summarized. Unless otherwise specified, Baseline is defined as the last observed measurement, whether scheduled or unscheduled, prior to study drug administration. Safety and efficacy endpoints will be summarized by treatment group and the active treatment groups pooled. Continuous variables will be summarized using the number of patients with data (n), mean, SD, median, minimum, and maximum. Selected continuous variable summarized using frequency counts and percentages.

The statistical analysis plan (SAP) will provide further details for statistical methodology. If the statistical analyses described in the final SAP and final protocol differ, the statistical analyses in the SAP will be used for the analyses presented in the clinical study report (CSR). Substantive changes from the analyses specified in the protocol will be described in the SAP and in the CSR.

All analyses will be performed using SAS® version 9.4 or higher, unless otherwise specified.

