### 9.3.3. Open-Label Safety Population

The open-label safety population will include all patients who are enrolled in the OLE Phase and take at least one dose of open-label study drug. Patients will be analyzed according to treatment received in the Double-Blind Treatment Phase (identical to the group they are reported under for the double-blind safety), active arms pooled, and overall.

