### 9.4.2.2. Open-Label Extension Analyses

Summary statistics will be reported for the measures of effectiveness at each visit where it is collected.

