## 10 Analysis Sets

**For the Double-Blind Treatment Phase:** Safety analyses will be conducted for the safety population. The mITT population will be used for the primary efficacy analysis. The PK population will be used for PK analyses. Patients will be analyzed according to their randomized treatment for efficacy assessments and according to the actual treatment received for safety assessments.

**For the OLE Phase:** The open-label safety population will be used.

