### 11.3.4 Extent of Study Drug Exposure

The descriptive statistics will be provided by treatment group for the Double-Blind Treatment Phase analyses and by treatment group received during the Double-Blind Treatment Phase and total for the OLE Phase analyses.

---

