### 11.4.4 Open-Label Extension Efficacy Analyses

The OLE efficacy parameters are:

- DSS
- ESS
- FSS
- Cogstate (Detection Test, Identification Test, One Back Test)
- MDHI Total score and sub-scores of sleep, fatigue and cognitive impairment
- CGI-S for EDS
- PGI-S for EDS

Actual and change from Baseline results in the OLE Phase will be summarized by using descriptive statistics at each open-label visit. Results will be tabulated by total. In addition, shift tables from baseline to each of the OLE visits will be provided for DSS, ESS, CGI-S and PGI-S.

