### 11.6 Safety Analyses

Safety analyses will be provided for the Double-Blind safety and open-label safety populations. All safety data will be listed and summarized. No formal statistics will be performed for the safety analyses.

For the Double-Blind Treatment Phase, summaries will be presented by treatment arms. For the OLE Phase, results will be tabulated by treatment received during the Double-Blind Treatment Phase (including active arms pooled) and overall.

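### SAP 6.1 puts all open-label patients in one Total group while SAP 11.6 and 11.3.4 report them by double-blind arm, and the Total-only effectiveness tables in 11.4.4 mix new with sustained response

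*SAP*

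**What the plan says.** The SAP sets the OLE grouping in several places:

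- SAP 6.1, for OLE reporting without restriction to any data type: "all patients will be analyzed as a single group, which will be labelled" Total. The reason given is that everyone follows the same three-week titration towards the same target dose.
- SAP 11.6, for OLE safety: "results will be tabulated by treatment received during the Double-Blind Treatment Phase (including active arms pooled) and overall".
- SAP 11.3.4, for exposure: "by treatment group received during the Double-Blind Treatment Phase and total for the OLE Phase analyses". No pooled active column is named.
- SAP 11.4.4, for OLE effectiveness: "Results will be tabulated by total".
- SAP 11.1.2, for important protocol deviations: total only in the OLE.

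SAP 10 says of the OLE: "The open-label safety population will be used". SAP 10.3 defines that population without naming a grouping. SAP 9.3 keeps the pre-treatment baseline of the double-blind phase as the OLE baseline.

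In the protocol, 9.3.3 says of the open-label safety population: "Patients will be analyzed according to treatment received in the Double-Blind Treatment Phase", with pooled active and overall added. The general rule in 9.1 is: "Safety and efficacy endpoints will be summarized by treatment group and the active treatment groups pooled". The section on OLE analyses, 9.4.2.2, says only: "Summary statistics will be reported for the measures of effectiveness at each visit where it is collected". The synopsis describes the by-arm analysis of the primary endpoint and then says that OLE effectiveness visits will be handled in a similar way.

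**The concern.** There are two separate problems.

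The first is that the SAP contradicts itself. Read literally, 6.1 calls for one column in every OLE table, whereas 11.6 and 11.3.4 call for a column per double-blind arm. A programmer cannot tell which safety and exposure tables to build. SAP 6 and protocol 9.1 let the SAP prevail over the protocol, but that does not help when both instructions stand in the SAP.

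The second is one of interpretation. Long-term safety and effectiveness is a named secondary objective. OLE effectiveness is summarised as change from a baseline taken before any study drug. Patients from all three arms may enter the OLE, so a single Total combines patients who have just begun pitolisant with patients who have taken it since Day 1. From that column alone, a reader cannot tell whether an early response has been held or whether former placebo patients have newly responded. The reason given in 6.1 covers the dosing schedule within the OLE but not exposure before it.

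**Working it through.** **Which instruction applies to which OLE table**

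| OLE output | SAP 6.1 | Specific SAP section | Agree? |
|---|---|---|---|
| Safety | Total | 11.6: by arm, pooled active, overall | No |
| Exposure | Total | 11.3.4: by double-blind group, total | No |
| Effectiveness | Total | 11.4.4: total | Yes |
| Protocol deviations | Total | 11.1.2: total | Yes |

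The contradiction is confined to safety and exposure. For effectiveness the SAP is consistent, and the question is whether the choice serves the objective.

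**Share of former placebo patients in the Total**

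Inputs: about 30 patients randomised 1:1:1 (protocol 3.1.1), so about 10 per arm. The documents give no OLE entry rate; 60% to 100% per group is assumed.

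- Equal entry: 10 / 30 = 33%.
- Placebo 60%, active 100%: 6 / (6 + 20) = 23%.
- Placebo 100%, active 60%: 10 / (10 + 12) = 45%.

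**Days on pitolisant at each OLE effectiveness visit**

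Inputs: first double-blind dose on Day 1 and first open-label dose on Day 78 (protocol 3.1.1.2 and 3.1.1.3); visits on Days 99, 279 and 459. Nominal days and uninterrupted dosing are assumed, and the visit day is counted. For a visit on day d, former active patients have d days and former placebo patients have d − 78 + 1.

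| Visit | Former placebo | Former active | Ratio |
|---|---|---|---|
| Visit 6, Day 99 | 99 − 78 + 1 = 22 | 99 | 22% |
| Visit 7, Day 279 | 279 − 78 + 1 = 202 | 279 | 72% |
| Visit 8, Day 459 | 459 − 78 + 1 = 382 | 459 | 83% |

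The gap is always 77 days, the length of the double-blind phase. Relative to total exposure it matters most at Visit 6.

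**What pooling does to the mean**

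Let mean change from baseline be a in former active patients and p in former placebo patients, with g = a − p. With equal entry, the Total mean is (1/3)p + (2/3)a.

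- Total minus a = −g/3.
- Total minus p = +2g/3.

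The Total therefore misses the former active mean by one third of the gap and the former placebo mean by two thirds. The documents do not give g, so this cannot be turned into scale points.

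**The case against.** The case for leaving the plan largely alone has several parts.

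*The single group is a disclosed change.* It stands under the SAP's heading for changes from the protocol, with a reason. This is right: the difference from protocol 9.3.3 is not an error in itself. Disclosure does not cure the conflict with 11.6 and 11.3.4.

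*Adverse events will not be pooled.* A reader might infer that the plan hides first-exposure events in former placebo patients. The documents do not support that as stated. Section 11.6, the operative safety section, separates the arms, and all adverse events are also listed. Such events would be lost in the summary tables only if 6.1 overrides 11.6. That is a conditional risk, created by the ambiguity.

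*Protocol 9.3.3 does not govern effectiveness.* A reader might take it as requiring by-arm effectiveness tables. It defines a safety population, and 9.4.2.2 names no grouping. Better support comes from the general rule in 9.1, which covers efficacy as well as safety, and from the synopsis. Even 9.1 is open to the reply that everyone is on one treatment in the OLE.

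*The mixing fades.* A reader might conclude that the Total cannot be read as a long-term effect at all. That goes too far. All patients follow the same OLE titration schedule, and by Visit 8 former placebo patients have 83% of the exposure of the others. The problem is sharpest at Visit 6, at the end of titration.

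*The tables are descriptive and the cells small.* This stands, and it limits how serious the point is. It is not a reason to omit the columns, since the overall column would stay.

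**Conclusion.** The point holds in two parts of different strength.

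SAP 6.1 against 11.6 and 11.3.4 is wrong as written. The instructions for OLE safety and exposure tables are incompatible, and nothing in the SAP says which governs. This rests on the text alone.

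The Total-only effectiveness tables in 11.4.4 are internally consistent but poorly suited to the long-term objective, so changing them is a cheap improvement. The 6.1 conflict does not cause this: 6.1 and 11.4.4 agree. About one third of the Total would be former placebo patients with equal OLE entry, or 23% to 45% under the assumed entry rates. The direction and size of the effect on the mean depend on a between-group difference that the documents do not give.

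Only the descriptive reporting of the OLE is affected. The primary comparison and the other double-blind analyses do not depend on it.

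**What to change.** 1. In SAP 6.1, delete the single-group sentence, or narrow it so that it no longer covers safety and exposure and agrees with 11.3.4 and 11.6.
2. In SAP 11.4.4, tabulate OLE effectiveness by double-blind arm (placebo, lower dose, higher dose), pooled active and overall.
3. For consistency, use the same columns in 11.1.2, and add the pooled active column in 11.3.4.

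If only step 1 is taken, the contradiction is removed but the effectiveness tables still mix new with sustained response.

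The cost is SAP wording and extra table columns. No new data or model is needed, and the sample size does not change. The downside is small cells: at full OLE entry about 10 patients per arm and 20 pooled active, fewer after non-entry and dropout. That is tolerable in descriptive tables that keep the overall column. SAP 9.4 gives the OLE its own data cut, so the double-blind reporting is untouched.
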